2. STUDY DESIGN

This study is a Phase 2, multicenter, randomized, double-masked, parallel-group clinical trial in subjects with dry eye disease (DED). Subjects 18 years of age and older with a diagnosis of dry eye disease who meet all study entry criteria will be enrolled. The investigator and his/her staff will not know which study medication the subject is receiving but will be able to determine this in the event of an emergency.

Prior to enrollment, the study will be discussed with prospective subjects and those wishing to enter will be asked to give written informed consent. Informed consent will be obtained prior to any study related procedures being performed. Once informed consent has been obtained, the subjects will be questioned regarding their medical history to determine whether or not they are in satisfactory health to enter the study and to determine if they meet the specific entry criteria.

During the screening period (Day -14 to Day 0) of the study, subject eligibility will be determined. All eligibility criteria must be met for randomization into the study. Subjects who meet all inclusion and none of the exclusion criteria at the Screening Visit may proceed directly to Visit 2 on Day 0 for randomization. Subjects who fail screening may be re-screened once and should repeat Screening Visit 1 (Day -14 to Day 0) within 30 days of the original screening visit. Approximately 280-350 subjects at approximately 40 investigational sites located in the United States who meet all study entry criteria will be randomized at Visit 2 (Day 0) in a balanced ratio to 1 of 7 treatment groups:

- SURF-100 (0.3% MPA/0.01% BSP)
- 0.1% MPA
- 0.3% MPA
- 0.01% BSP
- Vehicle
- 0.05% cyclosporine ophthalmic emulsion
- 5% lifitegrast ophthalmic solution

The study eye will be determined by the investigator based on the results of the ophthalmic examination. Some subjects may have both eyes qualify for the study. In these cases, data from the eye with the worst combined clinical signs and symptoms score at Visit 2 (Day 0), or at Visit 1 (Day -14 to Day 0) if Visit 2 is <5 days after Visit 1, will be identified as the study eye and will be analyzed for safety and efficacy throughout the study. If the total score is the same for both

eyes, the right eye will be designated as the study eye and data from the right eye will be analyzed for safety and efficacy.

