4.1. Inclusion Criteria

The following are inclusion criteria for prospective study subjects to be confirmed at Visit 1 (Day -14 to Day 0) prior to randomization.

1. Adults at least 18 years of age at the time of the Screening visit.
2. Willing and able to read, sign, and date the informed consent form (ICF) after the nature of the study has been explained and any questions have been answered, and prior to initiation of any study procedures or exams.
3. Willing and able to comply with all study procedures and attend all study visits.
4. Willing to suspend use of tear substitutes at least 72 hours prior to Visit 2 (Day 0) through Visit 7 (Day 98).
5. Best corrected visual acuity (BCVA) of 0.7 log of the minimum angle of resolution (logMAR) or better (Snellen equivalent score of 20/100 or better) in each eye at Visit 1 (Day -14 to Day 0).

6. Subject-reported history of dry eye in both eyes.
7. Meeting ALL of the following criteria in the same eye at Visit 1 (Day -14 to Day 0) and meeting ALL of the following criteria in the same eye at Visit 2 (Day 0) if Visit 2 is performed >5 days after Visit 1:
 - a) Minimum score of greater than or equal to 5 but less than or equal to 9 on UNC DEMS questionnaire.
 - b) Schirmer Tear Test (with anesthesia) equal to or less than 10 mm, but more than 1 mm
 - c) TBUT: Equal to or less than 5 seconds
8. A negative urine pregnancy test if female and of childbearing potential (those who are not surgically sterilized [bilateral tubal ligation, hysterectomy, or bilateral oophorectomy] or post-menopausal [12 months after last menses] or premenarchal) and must have used adequate birth control throughout the study period (through Visit 7 [Day 98]). Adequate birth control is defined as hormonal-oral, implantable, injectable, or transdermal contraceptives; mechanical - spermicide in conjunction with a barrier such as condom or diaphragm; intrauterine device; abstinence; or surgical sterilization of male partner.

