8. CLINICAL ASSESSMENTS/EXAMINATION PROCEDURES

Subject Completed Assessments:

UNC DEMS Questionnaire: The UNC DEMS will be completed by subjects at Visit 1 (Screening; Day -14 to Day 0) and only at Visit 2 (Day 0) if Visit 2 is >5 days following Visit 1. The UNC DEMS will also be completed by subjects at Visit 3 (Day 7) through Visit 7 (Day 98).

Dosing Diary with Drop Comfort Questionnaire: Subjects will be given a Dosing Diary with Drop Comfort Questionnaire to record study drug dose instillation dates and times for each dose, as well as to record their responses to the Drop Comfort Questionnaire every 7 days during the dosing period (Day 0 to Day 83).

Investigator Assessments:

Best-Corrected Visual Acuity (BCVA): BCVA will be performed in both eyes at Visit 1 (Screening; Day -14 to Day 0) and only at Visit 2 (Day 0) [prior to randomization] in both eyes if Visit 2 is >5 days following Visit 1. BCVA will also be performed in treated eyes at Visit 3 (Day 7) through Visit 7 (Day 98). Log of the minimum angle of resolution [logMAR] score using ETDRS [Early Treatment Diabetic Retinopathy Study] chart will be used to measure BCVA. Performing a pinhole test is allowed as long as its use remains consistent for the same subject throughout all study visits.

Biomicroscopy: Slit lamp biomicroscopy will be performed to observe the overall health of the eye, including the lid/lashes, conjunctiva, cornea, anterior chamber, iris, and lens. This will be performed in both eyes at Visit 1 (Screening; Day -14 to Day 0) and only at Visit 2 (Day 0) [prior to randomization] if Visit 2 is >5 days following Visit 1. Slit lamp biomicroscopy will also be performed in treated eyes at Visit 3 (Day 7) through Visit 7 (Day 98).

Ophthalmoscopy: An undilated ophthalmoscopy exam will be performed in both eyes at Visit 1 (Screening; Day -14 to Day 0) and in treated eyes at Visit 7 (Day 98).

Intraocular Pressure (IOP): IOP will be measured in both eyes at Visit 1 (Screening; Day -14 to Day 0) and only at Visit 2 (Day 0) [prior to randomization] if Visit 2 is >5 days following Visit 1. IOP will also be measured in treated eyes at Visit 3 (Day 7) through Visit 7 (Day 98).

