10. STATISTICAL ANALYSES

10.1. Randomization, Stratification, and Masking

Eligible subjects will be randomly assigned to each of treatment groups in a balanced ratio according to a validated SAS® computer-generated central randomization schedule. The randomization schedule contains the coded treatment assignments for each randomization number. The randomization plan will be based on the study design, number of treatment groups and number of sites.

The randomization schedule is generated by an un-masked statistician who is not affiliated with the study. The randomization schedule is shared with the Sponsor's designee responsible for final clinical packaging and labeling to allow for proper packaging and labeling of the study drug supply. Access to the randomization code will be strictly controlled according to the Sponsor designee's Standard Operating Procedures (SOPs).

The randomization is not unmasked until the study is complete and the database is locked. The Sponsor will confirm in writing that there are no regulatory or quality issues which preclude the unmasking of the study.

Unmasking of the randomization code prior to study completion due to a medical emergency will be managed in accordance with the Sponsor designee's SOP. All unmasked cases will be fully documented. Otherwise, the study mask will remain intact.

In this double-masked study, the investigator and his/her study staff, the subject (including caregiver, if applicable) and Sponsor/designee (other than as stated above) are masked to the identity of the study drug.

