11. EFFICACY

11.1. Primary Efficacy Analysis

Subjects with a 10% or more reduction in UNC DEMS score from baseline are defined as responders, and response rates at Visit 6 (Day 84) will be summarized by treatment group. All other subjects with non-missing data will be treated as non-responders. Further, subjects who received non-study therapeutic treatment for the signs and symptoms of dry eye at or prior to Visit 6 (Day 84) will be treated as non-responders (treatment failure) from the time of receiving non-study therapeutic treatment regardless of whether the UNC DEMS score is available at the relevant visit. For the ITT analysis, subjects with a missing UNC DEMS score at a visit will be imputed by the LOCF method. Therefore, there will be no missing data for ITT analysis. The response rate will be summarized at Visit 6 (Day 84) by treatment group, along with its 95% CI which will be estimated by Clopper-Pearson exact method. The response rate difference between SURF-100 and each of the comparison treatment groups will be reported as well, with 95% CI of the difference estimated by the method of Newcombe with continuity correction. The difference in response rate between SURF-100 and other comparison treatment groups will be compared by Fisher's exact method.

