11.2. Secondary Efficacy Analyses

Secondary Endpoint: Based on TBUT at Day 84:

Tear Break-Up Time will be assessed 3 times at each study visit for each subject. The mean of the 3 measurements will be used as the source data for the analysis.

Mixed Model for Repeated Measures (MMRM): The absolute change from baseline in TBUT at Day 84 is the one of the pre-specified secondary endpoints, and the treatment effect based on the absolute change from baseline in TBUT at Day 84 will be the focus of interest. The MMRM will include fixed effects of baseline TBUT, age, treatment, visit, and treatment by visit interaction. The least squares means of the absolute change from baseline in TBUT and their 95% CIs at Day 84 will be estimated from the MMRM model for each treatment group. The treatment effect, the difference of least squares means between SURF-100 and each of the comparison treatment groups, and its 95% CI and p-value comparing the treatment effect at each visit will be estimated from the model as well. This analysis is only applicable to study eye.

Secondary Endpoint: Based on Schirmer Tear Test (with Anesthesia) at Day 84:

Mixed Model for Repeated Measures (MMRM): The absolute change from baseline in Schirmer tear test score at Day 84 is one of the pre-specified secondary endpoints, and the treatment effect based on the absolute change from baseline in Schirmer tear test score at Day 84 will be the focus of interest. The MMRM will include fixed effects of baseline Schirmer tear test score, age, treatment, visit, and treatment by visit interaction. The least squares means of the absolute change from baseline in Schirmer tear test score and their 95% CIs at Day 84 will be estimated from the MMRM model for each treatment group. The treatment effect, the difference of least squares means between SURF-100 and each of the comparison treatment groups, and its 95% CI and p-value comparing the treatment effect at each visit will be estimated from the model as well. This analysis is only applicable to the study eye.

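### The primary responder comparison in section 11.1 leaves out baseline UNC DEMS, giving up a little precision and some protection against chance imbalance in arms of 40 to 50

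*Combined protocol and SAP*

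**What the plan says.** - **Endpoint (11.1):** "Subjects with a 10% or more reduction in UNC DEMS score from baseline are defined as responders". The rate is assessed at Day 84.
- **Comparison (11.1):** "The difference in response rate between SURF-100 and other comparison treatment groups will be compared by" Fisher's exact method. The difference gets a Newcombe interval with continuity correction. The section names no covariate, stratified test or adjusted supportive analysis.
- **Comparators:** sections 2 and 10.2 name vehicle, cyclosporine and lifitegrast in the primary endpoint. Section 11.1 reports SURF-100 against every other arm.
- **Size (2):** "Approximately 280-350 subjects at approximately 40 investigational sites located in the United States who meet all study entry criteria will be randomized" "in a balanced ratio to 1 of 7 treatment groups".
- **Randomisation (10.1):** "The randomization plan will be based on the study design, number of treatment groups and number of sites". Stratification by baseline score is not described.
- **Baseline score:** entry requires "Minimum score of greater than or equal to 5 but less than or equal to 9 on UNC DEMS questionnaire" (4.1), and the scale is given before dosing: "The UNC DEMS will be completed by subjects at Visit 1 (Screening; Day -14 to Day 0") (8). Section 10.6 takes the last value before the first dose as baseline.
- **Secondary endpoints (11.2), by contrast:** "The MMRM will include fixed effects of baseline TBUT, age, treatment, visit, and treatment by visit interaction". The Schirmer model has the same form, with its own baseline.

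**The concern.** Response is a fall from a score on which subjects were also selected. If that score carries visit-to-visit error, subjects who enter near 9 will tend to fall and those who enter near 5 will tend to rise, whatever the treatment. Baseline would then predict response. Neither the randomisation nor the primary analysis, as described, takes account of it.

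Two things are at stake. The interval for each difference is somewhat wider than the collected data allow. And if the SURF-100 arm happens to start higher or lower than the others, every comparison moves in the same direction, because all of them share that arm. Section 11.2 shows that the plan accepts baseline adjustment, and no reason is given for leaving it out of the analysis that carries the main conclusion. An adjustment added after unmasking, once an imbalance has been noticed, would be open to challenge.

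**Working it through.** **Stated figure.** The supplied text gives no power calculation, response rates, reliability or baseline SD for UNC DEMS, so there is no planned figure to reproduce. Everything below, apart from arm size and the 10% rule, rests on stated assumptions.

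**1. Arm size.** 280/7 = 40 and 350/7 = 50.

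**2. Does the 10% rule ask more of some subjects than of others?** Ten percent is 0.5 point at baseline 5 and 0.9 at baseline 9. If the scale is scored in whole points (not stated), a fall of 1 point is 1/5 = 20.0% at 5, 16.7% at 6, 14.3% at 7, 12.5% at 8 and 1/9 = 11.1% at 9. It meets the rule at every eligible baseline. The case therefore rests on regression to the mean.

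**3. Does baseline predict response?** Two measurement-error models were used, both with whole-point scores and entry at 5–9.
- *Model A:* pre-selection mean 6.5, SD 2, reliability 0.5–0.9, mean fall 0.5 or 1.5 points. Response rises with baseline in every scenario. At reliability 0.7 with a constant fall of 0.5, it goes from 37% at baseline 5 to 71% at 9. The share of outcome variance explained, R² = Var[p(B)] / [p(1−p)], is 0.01–0.11.
- *Model B:* mean 6.5, true-severity SD 1.0–1.5, measurement SD 1.0–1.5, mean fall 0.7. Response goes from 31–41% at baseline 5 to 78–89% at 9, a slope of 9–15 percentage points per baseline point. R² is 0.056–0.137. If a random 10% are treatment failures, R² falls to 0.044–0.108.

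**4. Precision.** The relative narrowing of the interval is 1 − √(1 − R²).
- R² = 0.0104 gives 0.5%, R² = 0.0472 gives 2.4%, and R² = 0.137 gives 7.1%. The range is about 0.5–7%.
- A simulation of a standardised logistic estimate (60% v 40%, baseline uniform on 5–9) gave these mean Wald widths:

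| Odds ratio per baseline SD | n=40: crude → adjusted | n=50: crude → adjusted |
|---|---|---|
| 1.5 | 0.424 → 0.421 | 0.380 → 0.376 |
| 2 | 0.424 → 0.407 | 0.380 → 0.364 |
| 3 | 0.424 → 0.381 | 0.380 → 0.341 |

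These are about 1%, 4% and 10% narrower. Nothing in the documents supports an odds ratio as large as 3. With no prognostic value (odds ratio 1), the adjusted interval is about 1% wider.

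**5. Chance imbalance.** Assume a baseline SD of 1.25. The SD of the difference in baseline means is 1.25·√(2/n), which is 0.280, 0.264 and 0.250 at n = 40, 45 and 50. For k comparisons sharing one arm, P(at least one beyond 0.5 point) = 1 − ∫φ(z)[Φ(z+c) − Φ(z−c)]^k dz, with c = 0.5/(1.25/√n).

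| n per arm | one comparison | three named | all six |
|---|---|---|---|
| 40 | 7.4% | 17.9% | 28.8% |
| 45 | 5.8% | 14.3% | 23.5% |
| 50 | 4.6% | 11.5% | 19.1% |

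At Model B's slope, an imbalance of 0.5 point moves the crude difference by 0.5 × 9 = 4.5 to 0.5 × 15 = 7.5 percentage points. The typical shift is smaller. Its SD is SD[p(B)]·√(2/n). For the 37%-to-71% case (p = 0.524) this is √(0.0472 × 0.524 × 0.476) × √(2/40) = 0.1085 × 0.2236 = 2.4 points. Across Model A it is 0.7–3.5 points.

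**6. Scale.** At 60% v 40%, the planned Newcombe interval runs from −0.035 to 0.408 (width 0.443) at n=40 and from −0.009 to 0.388 (width 0.397) at n=50. Without the continuity correction the widths are 0.411 and 0.371, so the correction adds 0.443/0.411 − 1 = 8% and 0.397/0.371 − 1 = 7%.

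**7. Adjustment or exact test?** Simulated rejection at 60% v 40%, n=40, odds ratio 1.5–3: Fisher 35–37%, unadjusted Wald 44–47%, adjusted 45–54%. Under the null (50% v 50%, odds ratio 1.5): Fisher 3.3–3.4%, adjusted 5.0–5.4%.

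**The case against.** The strongest reply is that nothing is broken. A crude comparison of randomised arms is unbiased, and its 95% interval already allows for chance baseline imbalance. The wider interval and the shifted estimate are largely one loss of precision seen from two sides. That stands, so the point concerns efficiency and pre-specification only.

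The gain is also small. A few percent of width is usually less than the 7–8% that the continuity correction adds, and exact methods are a defensible choice for arms of 40–50 in Phase 2. Covariates in a repeated-measures model for a continuous change do not oblige the same for a binary endpoint. Treatment failures, who are non-responders whatever their score, weaken the link with baseline. All of this stands. It argues for keeping the exact analysis, but it does not argue against a nearly costless adjusted one beside it.

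A reader might go further in three ways that the documents do not support:
- That baseline sets a harder target for some subjects. The scoring increment is not stated, and on whole points a 1-point fall suffices at every eligible baseline.
- That the imbalance risk is 29%, 23% and 19%. That counts all six comparisons, whereas the endpoint names three.
- That adjustment would recover the power lost to Fisher's test. For weak to moderate prognostic strength, most of that gain comes from leaving the exact test.

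**Conclusion.** The point holds as a modest, nearly free improvement. The primary comparison is unadjusted, baseline UNC DEMS is available, and regression to the mean probably makes it prognostic. Under whole-point scoring and the assumed reliabilities, adjustment narrows the interval by about 0.5–7%, and it costs about 1% if baseline turns out not to matter. At an assumed baseline SD of 1.25, at least one named comparison is out of balance by more than 0.5 point in about 18%, 14% and 11.5% of trials at 40, 45 and 50 per arm. A reader might infer that the planned result would be biased or its error rate inflated. It would not: the crude analysis is valid, and Fisher's test is conservative. Confidence in the direction is good. Confidence in the size is limited, because the documents give neither the reliability of the score nor the expected response rates.

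**What to change.** In section 11.1, pre-specify one logistic model for Day 84 response over all seven arms, with treatment and continuous baseline UNC DEMS. Age may be added to match section 11.2, but no calculation here supports it. Use the same responder, treatment-failure and LOCF rules as the planned analysis. Average the predictions over the trial population to give a marginal risk difference with 95% CI for SURF-100 against each comparator. Report it beside the planned Newcombe and Fisher results, and state before unmasking which of the two carries the primary conclusion.

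The cost is SAP wording and one more model, with no new data. The downsides are that the model's interval is a large-sample one and that it assumes a common baseline slope across arms, which is why the exact analysis is kept.

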11.2. Secondary Efficacy Analyses

Secondary Endpoint: Based on TBUT at Day 84:

Tear Break-Up Time will be assessed 3 times at each study visit for each subject. The mean of the 3 measurements will be used as the source data for the analysis.

Mixed Model for Repeated Measures (MMRM): The absolute change from baseline in TBUT at Day 84 is the one of the pre-specified secondary endpoints, and the treatment effect based on the absolute change from baseline in TBUT at Day 84 will be the focus of interest. The MMRM will include fixed effects of baseline TBUT, age, treatment, visit, and treatment by visit interaction. The least squares means of the absolute change from baseline in TBUT and their 95% CIs at Day 84 will be estimated from the MMRM model for each treatment group. The treatment effect, the difference of least squares means between SURF-100 and each of the comparison treatment groups, and its 95% CI and p-value comparing the treatment effect at each visit will be estimated from the model as well. This analysis is only applicable to study eye.

Secondary Endpoint: Based on Schirmer Tear Test (with Anesthesia) at Day 84:

Mixed Model for Repeated Measures (MMRM): The absolute change from baseline in Schirmer tear test score at Day 84 is one of the pre-specified secondary endpoints, and the treatment effect based on the absolute change from baseline in Schirmer tear test score at Day 84 will be the focus of interest. The MMRM will include fixed effects of baseline Schirmer tear test score, age, treatment, visit, and treatment by visit interaction. The least squares means of the absolute change from baseline in Schirmer tear test score and their 95% CIs at Day 84 will be estimated from the MMRM model for each treatment group. The treatment effect, the difference of least squares means between SURF-100 and each of the comparison treatment groups, and its 95% CI and p-value comparing the treatment effect at each visit will be estimated from the model as well. This analysis is only applicable to the study eye.

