Conjunctival Hyperemia Assessment: Conjunctival hyperemia will be assessed in both eyes at Visit 1 (Screening; Day -14 to Day 0) and only at Visit 2 (Day 0) [prior to randomization] if Visit 2 is >5 days following Visit 1. Conjunctival hyperemia will also be assessed in the treated eye(s) at Visit 3 (Day 7) through Visit 7 (Day 98).

Tear Break-up Time (TBUT): TBUT will be conducted in both eyes at Visit 1 (Screening; Day -14 to Day 0) and only at Visit 2 (Day 0) [prior to randomization] if Visit 2 is >5 days following Visit 1. TBUT will also be measured in the treated eye(s) at Visit 3 (Day 7) through Visit 7 (Day 98).

Fluorescein Corneal Staining: Fluorescein corneal staining will be conducted in both eyes at Visit 1 (Screening; Day -14 to Day 0) and only at Visit 2 (Day 0) if Visit 2 is >5 days following Visit 1. Fluorescein corneal staining will also be measured in the treated eye(s) at Visit 3 (Day 7) through Visit 7 (Day 98).

Conjunctival Staining: Conjunctival staining using fluorescein dye will be conducted in both eyes at Visit 1 (Screening; Day -14 to Day 0) and only at Visit 2 (Day 0) if Visit 2 is >5 days following Visit 1. Conjunctival staining will also be measured in the treated eye(s) at Visit 3 (Day 7) through Visit 7 (Day 98).

Schirmer Tear Test: Schirmer tear tests will be conducted with anesthesia in both eyes at Visit 1 (Screening; Day -14 to Day 0) and only at Visit 2 (Day 0) if Visit 2 is >5 days following Visit 1. Schirmer tear tests (with anesthesia) will also be conducted in the treated eye(s) at Visit 3 (Day 7) through Visit 7 (Day 98) to assess aqueous production.

Adverse Events and Concomitant Medications: At each study visit, subjects will be queried for new adverse events and, if applicable, previously unresolved adverse events. Also, concomitant medications will be documented.

Diary: At Visit 2 through Visit 6 (Day 0 through Day 84), subjects' Dosing Diaries will be reviewed and compliance with study drug dosing and completion of the Drop Comfort Questionnaire will be evaluated.

Biomicroscopy and ophthalmoscopy study examinations should be performed by the same board-certified ophthalmologist or a board-certified or state licensed optometrist (that would allow them legally to diagnose and treat patients independently) from visit to visit. All other ratings and procedures should be performed by the same examiner from visit to visit whenever possible.

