10.5. Statistical Methods: General Considerations

All final statistical analyses will be performed after the study database has been locked, unmasked, and released for statistical analysis. All tables, statistical analyses, figures, and subject data listings will be generated using SAS® Version 9.4 or later (SAS Institute Inc., Cary, North Carolina, United States of America).

All data in the database will be presented in the data listings. Unless otherwise stated, all listings will be sorted by treatment group, subject number and assessment visit, as appropriate.

Unless otherwise stated, continuous variables will be summarized using descriptive statistics including number of non-missing observations (n), mean, standard deviation (SD), median, minimum and maximum values. The minimum and maximum values will be presented to the same number of decimal places as the eCRF or laboratory reported data; mean, SD, and median will be presented to one more decimal place than the source data.

Categorical variables will be summarized with frequency counts and percentages. The population size (N for sample size and n for available data) and the percentage (of available data) for each class of the variable will be presented. Percentages will be rounded to one decimal place, with the denominator being the number of patients in the relevant population, unless otherwise stated.

Only data from nominal protocol scheduled visits will be included in the summary tables. Data

from unscheduled visits will not be included in the summary tables but will be included in the figures and listings.

It should be noted that in this study the analysis unit is subject. When data from both eyes are available, data will not be pooled together for the analysis because eyes from the same subject are not independent samples. Statistical analysis generally requires independent samples. Each subject has a designated study eye as per the protocol. Therefore, separate analysis will be conducted for study eye and fellow eye as appropriate.

All confidence intervals (CIs) of the parameter estimates will be two-sided and at the significance level of 0.05 unless otherwise stated.

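### Both secondary MMRMs fit one baseline slope for all visits; a baseline-by-visit term is a cheap refinement that may sharpen the Day 84 contrast slightly

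*Combined protocol and SAP*

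**What the plan says.** Section 11.2 specifies two MMRMs on absolute change from baseline in the study eye. For TBUT: "The MMRM will include fixed effects of baseline TBUT, age, treatment, visit, and treatment by visit interaction". For Schirmer: "The MMRM will include fixed effects of baseline Schirmer tear test score, age, treatment, visit, and treatment by visit interaction". The treatment effect may differ by visit, but the baseline coefficient may not.

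The target is Day 84. For TBUT, "the treatment effect based on the absolute change from baseline in TBUT at Day 84 will be the focus of interest", with parallel wording for Schirmer. The models also report each treatment difference with "its 95% CI and p-value comparing the treatment effect at each visit will be estimated from the model as well".

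Section 11.2 does not list the visits that enter the model. Section 8 schedules the measurements: "TBUT will also be measured in the treated eye(s) at Visit 3 (Day 7) through Visit 7 (Day 98"), and the same visits for Schirmer. A five-visit model (Days 7, 30, 60, 84 and 98) is therefore the natural reading, but it is an inference. A four-visit model ending at Day 84 is not ruled out.

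On size, Section 2 plans "Approximately 280-350 subjects at approximately 40 investigational sites located in the United States", randomised "in a balanced ratio to 1 of 7 treatment groups". That is 280/7 = 40 to 350/7 = 50 per arm.

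**The concern.** In an MMRM, baseline adjustment removes the most variance at a visit when that visit has its own baseline slope. With a main effect only, the model estimates a compromise slope over all modelled visits and uses it at Day 84. The visits run from one week after first dose to two weeks after dosing stops, so a constant slope is an assumption that the plan makes without comment.

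If the assumption fails, two things are at stake. The TBUT and Schirmer differences at Day 84 keep some residual variance that could have been removed. And when subjects leave before Day 84, the model fills the gap partly through a baseline slope that is wrong for Day 84. Section 10.4 says missing data are in general not imputed, so the model itself carries that burden.

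**Working it through.** **Plan's own figure.** There is none to reproduce. The text gives no SD, effect size, power or baseline correlation for TBUT or Schirmer. All slopes, SDs and correlations below are assumptions.

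**Formula.** Let g be the vector of true visit-specific slopes of change on baseline and S the within-subject residual covariance. With treatment-by-visit in the model and complete data, the common slope settles at b = (1'S⁻¹g)/(1'S⁻¹1). The Day 84 contrast variance is then multiplied by

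VI = 1 + (g84 − b)² × sx²/se²,

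where sx is the baseline SD and se the Day 84 residual SD. If all slopes are equal, VI = 1.

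**Worked cases.** With compound symmetry and equal residual variances, b is the plain mean of the slopes. Four visits:

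- *Moderate drift*, slopes −0.3, −0.4, −0.5, −0.6: b = −0.45 and (g84 − b)² = 0.0225. With sx = se, VI = 1.0225 (SE +1.1%). With sx = 2.5 and se = 4, VI = 1 + 0.0225 × 6.25/16 = 1.0088 (SE +0.44%).
- *Strong drift*, slopes −0.2, −0.4, −0.6, −0.8: b = −0.50 and (g84 − b)² = 0.09. With sx = se, VI = 1.09 (SE +4.4%). With sx = 1 and se = 2, VI = 1.0225 (SE +1.1%).

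**Range over four or five visits, compound-symmetric or AR(1)-type correlation, and several SD ratios.** The power column starts from 81.2% (45 per arm, true difference 0.6 residual SD, two-sided 0.05).

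| Assumed drift in slope to Day 84 | SE loss | Power |
|---|---|---|
| None | 0% | 81.2% |
| Mild (−0.40 to −0.55) | 0.04–0.3% | – |
| Moderate (−0.3 to −0.6) | 0.2–1.1% | 80.4–81.1% |
| Strong (−0.2 to −0.8) | 0.7–4.4% | 77.8–80.7% |
| Extreme (0 to −0.9) | 1.6–9.7% | 73.7–80.0% |

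**In subjects.** A grid of 497 assumed configurations (correlation with baseline 0.5–0.7 at Day 7 and 0.2–0.4 at Day 84) gives a median variance loss of 1.5% and an interquartile range of 0.4–4.0%. Per arm of 50 that is 0.015 × 50 = 0.75 subject, with a range of 0.004 × 50 = 0.2 to 0.040 × 50 = 2.

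**Direction.** The slope of the follow-up value on baseline is correlation × (follow-up SD/baseline SD). If correlation falls from 0.6 to 0.3 while the SD ratio stays at 1, the slope falls from 0.60 to 0.30. If the ratio rises to 1.5, the Day 84 slope is 0.3 × 1.5 = 0.45. If it rises to 2, the slope is 0.3 × 2 = 0.60 and there is no net drift. The matching variance losses are roughly 2–19% (the top from an extreme correlation setting), 0.5–3.9%, and at most 0.06%. Eligibility caps baseline (TBUT at most 5 s, Schirmer above 1 to 10 mm) but not follow-up, so a rising ratio is plausible. A larger rise would leave the common slope too shallow at Day 84.

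**Simulation, complete data** (7 arms, 40 or 50 per arm, 5 visits, 1,500 runs per setting). The ratio of the contrast's SD, common slope to visit-specific slopes, was 0.999–1.000 with equal slopes, 1.000–1.011 with moderate drift and 1.004–1.033 with strong drift. For the common-slope model the mean error was near 0 and rejection under the null was 3.7–5.3%.

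**Simulation, dropout** (two large arms, no true effect, correlation falling from 0.6 to 0.3, constant SD). With 15% dropout unrelated to baseline, neither model was materially biased. With 15% unrelated dropout in one arm and 21% concentrated at low baseline in the other, the common slope was biased by about 0.04 SD and the visit-specific model by under 0.005. With opposite baseline-related dropout of about 21% in each arm, the figures were about 0.08 and 0.002 SD. A separate check gave 0.02–0.05 SD when the dropout pattern differed between arms, and no material bias when it was the same.

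**Cost of the added term when slopes are equal.** With five visits it adds 4 parameters. At N = 280 the variance factor is at most about 1 + 1/270 = 1.0037, so the SE rises by about 0.18%. Simulated model SEs rose by 0.15–0.18%. The t quantile moves from 1.9688 to 1.9689.

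**The case against.** The best defence is that a main-effect baseline term is a legitimate model and nothing in the documents shows that the slope drifts. The loss is conditional, and the grid percentiles count chosen configurations rather than probabilities; that grid contains only falling correlations. Under mild drift the gain is of the same order as the small cost of the added term. These are secondary endpoints in a Phase 2 trial with no stated power target, so no documented operating characteristic is missed. All of this stands, and it is why the point is a refinement and not an error.

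The defence on missing data stands in part. Section 10.5 places early-discontinuation data in the Day 84 assessment for by-visit summaries. If that rule also governs the MMRM, fewer Day 84 values are missing, and some of those present come from earlier times. The plan does not say whether it does.

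A reader might infer more: that the models certainly lose precision, that the pooled slope must be too steep at Day 84, that several subjects per arm are wasted, or that the secondary p-values are invalid. The documents support none of these. The loss is zero under equal slopes, the direction depends on unstated SDs, the grid median is under one subject per arm, and the simulated error rate stays near 5%.

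**Conclusion.** The point holds as a small, conditional efficiency issue. Both models as written impose one baseline slope on every modelled visit while Day 84 is the focus. If the slope changes over visits, the Day 84 contrast loses typically about 0–4% in variance. Losses beyond that need strong drift and, in most cases, a baseline SD close to the residual SD; the eligibility caps limit the baseline SD. Validity with complete randomised data is not in question.

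The bias of about 0.02–0.08 SD arises only under assumed dropout that relates to baseline differently in the two arms. No dropout rate is given, so its relevance here cannot be sized. The five-visit model and the covariance structure are also assumptions, since Section 11.2 states neither. Severity: nice to have.

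**What to change.** In Section 11.2, add a baseline-by-visit interaction to both MMRMs, so that the fixed effects read: baseline, age, treatment, visit, treatment-by-visit and baseline-by-visit. It would help to list the modelled visits and the covariance structure in the same edit.

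The cost is one term in each of two models: 4 extra parameters each with five visits, or 3 with four. No new data are needed. The worst case, equal slopes, is an increase of under about 0.2% in the standard error. The change should be made before unmasking.
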